- 4. Subjects randomly assigned to the 30 mg/kg Q8w arm will receive REGN2222 on Day 1 and Day 57. Subjects randomly assigned to the single 30 mg/kg arm will receive REGN2222 on Day 1 and placebo on Day 57. Subjects randomly assigned to the placebo arm will receive placebo on Day 1 and Day 57.
- 5. No other vaccinations will be administered within 2 days before or after dosing of the study drug. Any subject who has had a positive RT -PCR RSV nasal swab result, either at the study central laboratory or at an outside institution in a CLIA-certified (or equivalent) laboratory, should not receive a second dose of study drug nor have postdose assessments completed on the day of dosing. The subject should, however, continue in the study and have all other assessments completed during subsequent visits. If the subject has had a positive RSV test using non-PCR assays or any RSV positive test including a RT-PCR test in laboratories that are not CLIA-certified (or equivalent), they should receive the second dose as planned. The study staff will contact the parent(s) or legal guardian(s) by telephone at the end of each dosing day and daily over 48 hours following a dose to inquire about any change in the subject's status.
- 6. On study drug dosing days, two vital signs assessments (temperature, blood pressure, pulse, and respiration) will be performed when the child is calm: once prior to blood sample collection (if applicable) and injection of study drug, and again 1 hour (±10 minutes) after completion of the injection. Dosing may only proceed if the subject is afebrile (rectal temperature ≤101°F (38.3°C) without the use of antipyretics in the preceeding 48 hours. If a subject's rectal temperature is ≥101°F (38.3°C) on a dose administration day then no dosing will occur (see Section 6.3.1.1 for temperature conversions). The subject will then be re-evaluated within 48 hours; if the subject's temperature is ≤101°F (38.3°C) without the use of antipyretics during the previous 48 hours then the schedule of assessments may be resumed. Conversely, if the subject's temperature is still ≥101°F (38.3°C) or the subject has received antipyretics in the previous 48 hours, then dosing of the subject will be permanently discontinued.
- 7. Physical examinations will be conducted before injection and after injection, and prior to discharge from the clinic at Visit 2 and Visit 4. Weight collection is not required post-injection.

Regeneron Pharmaceuticals, Inc.

Page 57 of 137

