2. INVESTIGATION PLAN

2.1. Study Design and Randomization

This is a Phase 3 study that will be conducted in 2 parts.

Part A was an open-label, single cohort, multicenter, PK study.

Part B is a randomized, placebo-controlled, 3-arm, multicenter study. In Part B, the sponsor (Regeneron Pharmaceuticals, Inc.) will provide permitted windows for prophylaxis of subjects in each geographical area based on historical data on the timing and duration of the RSV season. A total of 3 treatment arms (1 dose of REGN2222 and 1 dose of placebo; 2 doses of REGN2222; and 2 doses of placebo) with a total of 1515 subjects are planned in Part B and will be randomized in a 1:1:1 ratio (505 subjects in each arm for a total of 1010 assigned to receive REGN2222 [505 subjects in each of the 2 REGN2222 arms] and 505 subjects to receive placebo). Randomization will be stratified by region (North America or rest of the world) and GA (≤ 31 weeks, 6 days GA or from 32 weeks, 0 days to 35 weeks, 6 days GA).

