pre-specified hierarchical inferential approach (2-sided $\alpha=0.05$ for each statistical test; see Section 5.7.3), as opposed to the originally planned Bonferroni adjustment (2-sided $\alpha=0.025$ for each pairwise treatment comparison). Therefore, assuming approximately 1200 subjects are administered study drug, the comparison of the REGN2222 2-dose regimen to placebo will have approximately 87% power to detect the previously planned 60% reduction in medically attended RSV infections with a 2-sided significance level of 0.05.

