3.2. The Safety Analysis Set (SAF)

SAF includes all subjects (randomized or non-randomized) who receive any study drug. For all safety variables, subjects will be analyzed as treated. As-treated is defined as the actual number of REGN2222 doses received by a subject, ie, single dose of REGN2222, 2 doses of REGN2222, and placebo.

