5.8. Analysis of Safety Data

Safety and tolerability will be descriptively summarized, including AEs, clinical laboratory variables, physical exam, and vital signs for the SAF. The summary of safety results will be presented for the treatment groups of combined REGN2222 dose arms with the intent to maximize efforts to detect potential safety signals. The individual REGN2222 dose arms will also be presented with the intent to support the combined regimens. No formal inferential testing will be performed. Summaries will be descriptive in nature.

All safety analyses will be performed, unless otherwise specified, using the following common rules:

- The baseline value is defined as the last available value obtained up to the date and time of the first dose of study drug, unless otherwise specified.
- For clinical laboratory, physical exam, and vital signs variables, all measurements, scheduled or unscheduled, will be assigned to analysis windows defined in Appendix 11.3 in order to provide an assessment for Visit 3 to Visit 7 time points.
- For continuous safety parameters including central laboratory measurements and vital sign scores, descriptive statistics will be used to summarize results and change from baseline values by visit.
- A treatment-emergent Potential Clinically Significant abnormal value (PCSV) is a laboratory value or vital sign that was: normal at baseline but abnormal after treatment with study drug during the TEAE period, or: abnormal at baseline and worsened after treatment with study drug during the TEAE period. Thresholds for treatment-emergent PCSV in laboratory variables and vital signs are defined in Appendix 11.4. Treatment-emergent PCSV criteria will determine which subjects had at least 1 treatment-emergent PCSV, taking into account all assessments including unscheduled assessments. Subjects who had post-baseline PCSV during the TEAE period but missing baseline value will be regarded as having treatment-emergent PCSV. There are no universally accepted normal ranges for preterm infants. The ranges used to determine PCSV criteria are associated with full-term infants (except

for bilirubin) and consequently, the TEPCSV results are to be interpreted with caution.

The summary of safety results will be presented by treatment group (REGN2222 1 dose, REGN2222 2 doses, REGN2222 combined, and placebo).

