- TEAEs that occurred within 2 days after the second dose in subjects who received the second dose: All, study drug-related, and injection procedure-related TEAEs by SOC and PT.
- TEAEs that occurred within 7 days after either the first dose or the second dose (ie, post dose TEAE start date - dosing date ≤ 7): All, study drug-related, and injection procedure-related TEAEs by SOC and PT.
- TEAEs that occurred within 7 days after the first dose: All, study drug-related, and injection procedure-related TEAEs by SOC and PT.
- TEAEs that occurred within 7 days after the second dose in subjects who received the second dose: All, study drug-related, and injection procedure-related TEAEs by SOC and PT.
- Two event rate estimations adjusted by subject year of follow-up will be provided for all TEAEs by SOC and PT:
 - Total number of events divided by the total length of the TEAE period over all subjects in the SAF of each treatment group.
 - Total number of subjects with an event in question divided by the total length of the TEAE period. For a subject with event, the time from first dose to the first event will be counted towards the denominator. For a subject without event, the time from first dose to the end of the TEAE period will be counted towards the denominator.

The above TEAE summaries will present the number (n) and percentage (%) of subjects experiencing an TEAE by SOC and PT. Multiple occurrences of AEs of the same PT (or SOC) in the same subject will be counted only once for that PT (or SOC). For tables presenting severity of events, the worst severity will be chosen for subjects with multiple instances of the same event. Relatedness to study drug or injection procedure is according to investigator's opinion.

Primary SOCs will be sorted by decreasing frequency in the combined REGN2222 group. Within each primary SOC, PTs will be sorted by decreasing frequency in the combined REGN2222 group.

The description of TEAEs reported by $\geq 5\%$ of subjects in any treatment group will also be performed for demographic and baseline factors including: sex, chronological age (≤ 3 months, > 3 months), gestational age (≤ 31 weeks 6 days, ≥ 32 weeks 0 days and ≤ 35 weeks 6 days), and region.

Subject listings for deaths, all serious TEAEs, TEAEs leading to permanent treatment discontinuation, TEAEs with severity of 3/4/5/Severe/Life-Threatening/Fatal, and treatment-emergent AESIs will be provided.

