5.8.2. Analysis of Adverse Events of Special Interest and Preferred Terms of Interest for Identification of Hypersensitivity

Treatment emergent AESIs and PTs of interest for identification of hypersensitivity (as defined in Section 4.7.2) will be presented by SOC and PT, or by PT alone. The summaries will be sorted by decreasing incidence of PT within each SOC in the combined REGN2222 group if presented by SOC and PT. In addition, the following analyses will be performed to further characterize the safety profile in each treatment group:

- TEAEs that are PTs under the HLT of injection site reaction will be summarized by:
 - Number (and percentage) of subjects who experienced 1 vs. >1 events of injection site reaction.
 - Number (and percentage) of subjects who experienced at least one event of injection site reaction by highest severity.
 - Descriptive statistics including number of subjects, mean, median, standard deviation, minimum, Q1, Q3, and maximum will be provided for the following measures:
 - Number of events divided by the number of study drug injections each subject received. Note each dose of study drug can be administered via more than 1 injections according to the total volume of study drug determined by the subject's body weight.
 - Mean duration of events. The duration of an event is defined as (AE stop date - AE start date +1). If an AE is ongoing at the end of the study, the last visit date will be used in lieu of AE stop date. Mean duration is calculated as the duration averaged over all events experienced by a subject.
 - Number of days following the most recent study drug injection to the first event of injection site reaction.
 - Number of events and number (and percentage) of subjects with events that occurred within 2 days after dosing by PT. For subjects who did not receive the second dose, only those events that occurred up to Day 57 (Day 1 being the day when the first dose was administered) will be included.
 - Number of events and number (and percentage) of subjects with events that occurred beyond 2 days after dosing by PT. Only subjects who received the second dose will be included in this analysis.

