3. When parent(s) or guardian(s) take their child for medical attention outside of the study site, the parents/guardians are instructed to take the Medical Information Packet with them for use by their healthcare provider. Data on medically attended RSV infections will be collected for all subjects until Day 150.
4. Subjects randomly assigned to the 30 mg/kg Q8w arm will receive REGN2222 on Day 1 and Day 57. Subjects randomly assigned to the single 30 mg/kg arm will receive REGN2222 on Day 1 and placebo on Day 57. Subjects randomly assigned to the placebo arm will receive placebo on Day 1 and Day 57.
5. No other vaccinations will be administered within 2 days before or after dosing of the study drug. Subjects who have reached the primary endpoint should not receive additional doses of study drug. The study staff will contact the parent(s) or legal guardian(s) by telephone at the end of each dosing day and daily over 48 hours following a dose to inquire about any change in the subject's status.
6. On study drug dosing days, vital signs when the child is calm (temperature, blood pressure, pulse, and respiration) will be assessed prior to blood sample collection, prior to injection of study drug, and 1 hour (± 10 minutes) after completion of the injection. If a subject's rectal temperature is 101°F (38.3°C) or greater on the day of a planned dose administration day, no dosing will occur (see Section 6.3.1.1 of protocol for temperature conversions). The subject will be re-evaluated within 48 hours and if the subject's temperature is below 101°F (38.3°C) without the use of antipyretics during the previous 48 hours, the schedule of assessments may be resumed. If the subject's temperature is 101°F (38.3°C) or greater or the subject has received antipyretics in the previous 48 hours, dosing of the subject will be permanently discontinued.
7. Physical examinations will be conducted before injection and after injection, prior to discharge, from the clinic at Visit 2 and Visit 4. Weight collection is not required post-injection.
8. If the adverse event is considered a hypersensitivity or anaphylaxis reaction, then the adverse event will be assessed as outlined in Protocol Table 4.
9. If the adverse event is a hypersensitivity reaction that results in a rash, then a photo will be taken as part of the adverse event assessment (also see Protocol Table 4).

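### In acute safety tables limited to the second dose, the combined REGN2222 column counts Day 57 placebo injections with REGN2222 and shows about half the excess over placebo

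*SAP*

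**What the plan says.** The Day 57 product differs between the two REGN2222 arms. Protocol Table 2, footnote 4 (Section 6.1) states: "Subjects randomly assigned to the single 30 mg/kg arm will receive REGN2222 on Day 1 and placebo on Day 57". For the other arm, SAP 11.2 states: "Subjects randomly assigned to the 30 mg/kg Q8w arm will receive REGN2222 on Day 1 and Day 57".

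Safety columns are defined by subject and not by injection. SAP 3.2: "As-treated is defined as the actual number of REGN2222 doses received by a subject". SAP 5.8 then shows safety results in four columns: REGN2222 1 dose, REGN2222 2 doses, REGN2222 combined, and placebo. Results are "presented for the treatment groups of combined REGN2222 dose arms with the intent to maximize efforts to detect potential safety signals", and the individual arms are described as support. SAP 5.8.1 sorts adverse event tables by frequency in the combined group. SAP 5.8.2 does the same for hypersensitivity tables presented by system organ class and preferred term.

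SAP 5.8.1 includes tables of "TEAEs that occurred within 2 days after the second dose in subjects who received the second dose", the same for 7 days, and tables of all, drug-related and injection-procedure-related events after the second dose. No exception to the column layout is made for them. SAP 5.8.2 adds injection-site summaries, including "Number of events divided by the number of study drug injections each subject received", and counts of events within 2 days of dosing. These summaries are not split by first and second injection.

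**The concern.** Pooling the two REGN2222 arms is sound for the first injection, because both arms receive REGN2222 on Day 1. In a table restricted to the second injection, the 1-dose column holds infants who have just been injected with placebo, and the combined column adds them to infants who have just been injected with REGN2222.

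The Day 57 injection in the 2-dose arm is the only planned re-exposure to the antibody. Protocol 1.3 lists hypersensitivity and antidrug antibody formation among the potential risks. Protocol 7.2.4.2 defines the events of special interest as hypersensitivity reactions within 48 hours of exposure. No formal safety testing is planned, so a signal would be found by reading these displays. A reader who follows the SAP's stated lead column would see a weakened contrast in the tables where a reaction to re-exposure would appear.

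**Working it through.** **Inputs.** The plan gives no figure for this dilution. The one design figure needed is equal allocation: "will be randomized in a 1:1:1 ratio (505 subjects in each arm for a total of 1010 assigned to receive REGN2222" (SAP 2.1). For the reduced trial, SAP 2.2 works from "assuming approximately 1200 subjects are administered study drug", so 1200 / 3 = 400 per arm. As background, the planned arm size reproduces. A continuity-corrected chi-square comparison of 10% with 4%, at 2-sided 0.025 and 90% power, needs 480 per arm, and 480 / 0.95 = 505.3 against the stated 505. The documents give no acute reaction rates, so all rates below are assumptions.

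**Formula.** Let r2 be the acute reaction rate after a second REGN2222 injection and r0 the rate after placebo. Let w be the share of second-dose recipients in the combined column whose Day 57 injection was REGN2222.

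- Combined rate = w·r2 + (1 − w)·r0
- Combined excess over placebo = w·(r2 − r0)

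**Value of w.** With equal arms and equal second-dose uptake, w = 0.50. With assumed uptake of 85% in one arm and 95% in the other, w = 0.85 / 1.80 = 0.47 or 0.95 / 1.80 = 0.53.

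**Second-dose tables, w = 0.50, 400 per arm:**

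| r0 | r2 | Excess, 2-dose column | Combined rate | Excess, combined column |
|---|---|---|---|---|
| 0% | 1% | 1.0 point | 0.5% | 0.5 point |
| 0.5% (2/400) | 2.0% (8/400) | 1.5 points | 10/800 = 1.25% | 0.75 point |
| 1% (4/400) | 3% (12/400) | 2.0 points | 16/800 = 2.0% | 1.0 point |
| 2% (8/400) | 5% (20/400) | 3.0 points | 28/800 = 3.5% | 1.5 points |

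The excess is halved whatever the rates. The raw rate is halved only when r0 = 0.

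**The doubled denominator does not make up for it.** Illustrative power is Φ((d − 1.96·SE0) / SE1), where d is the difference in rates, SE0 uses the pooled rate and SE1 the separate rates. For 3% versus 1%:

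- 2-dose column: (0.0200 − 1.96 × 0.00990) / 0.00987 = 0.06, power 52%.
- Combined column: (0.0100 − 1.96 × 0.00784) / 0.00702 = −0.76, power 22%.

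For 5% versus 2% the figures are 64% and 28%. They only gauge visibility, since the SAP tests nothing here.

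**Tables covering either dose.** These also include the first injection, which is not diluted. If both REGN2222 injections carry the same excess (1% placebo, 3% REGN2222):

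- 2 doses: 1 − 0.97² = 5.91%
- 1 dose: 1 − 0.97 × 0.99 = 3.97%
- Combined: (5.91 + 3.97) / 2 = 4.94%
- Placebo: 1 − 0.99² = 1.99%
- Share of excess kept: (4.94 − 1.99) / (5.91 − 1.99) = 2.95 / 3.92 = 75%

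If only the second injection carries an excess, the 2-dose column shows 3.97 − 1.99 = 1.98 points and the combined column 0.99, which is half again.

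**Events per injection.** With one injection per dose and full uptake, the mean excess is (r − r0) in the 2-dose arm and (r − r0) / 2 in the 1-dose arm, where r is the rate after either REGN2222 injection. The combined column averages these and keeps 75%.

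**The case against.** The strongest reply is that the right contrast is already planned. Each second-dose table has a REGN2222 2 doses column beside placebo. The frequency cut-offs in SAP 5.8.1 apply to any treatment group, so a term common only in the 2-dose arm would still be shown. Events of special interest, serious events and events of Grade 3 or above are listed by subject. All of this stands. A reader might infer that the plan cannot see a reaction to a second dose. The documents do not support that.

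The columns also follow the stated as-treated rule. An infant in the 1-dose column did receive one REGN2222 dose. It would be wrong to call the columns mislabelled. They group by subject where these tables call for grouping by injection.

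Two further readings go too far:

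- **A quarter of the injections behind the combined per-injection rate are placebo.** The sum 400 / (800 + 400 + 400) = 25% counts doses. SAP 5.8.2 notes that a dose may need more than one injection depending on weight, so the share of injections cannot be derived.
- **The 1-dose arm can simply be pooled with placebo at Day 57 for precision.** The standard error would fall by about 13% (√(1/400 + 1/800) = 0.0612 against √(2/400) = 0.0707). However, the 1-dose infants have had prior exposure and may have circulating drug. Protocol 1.2.2.1 gives a mean adult half-life of up to 36 days, and 57 / 36 is about 1.6 half-lives. The pooled group would not be a clean placebo group for all events within 7 days.

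Finally, Protocol 9.5.3.2 itself calls for summaries by arm and for the combined arms, so dropping a column is a departure and has to be declared.

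**Conclusion.** The point holds for acute tables restricted to the second dose. There the combined column shows about half the excess over placebo (47% to 53% under the uptake range assumed). This rests on 1:1 allocation, broadly similar second-dose uptake, and a 1-dose arm whose Day 57 placebo injection carries the placebo reaction rate. Summaries covering either dose or events per injection are only partly diluted. They keep about 75% of the 2-dose excess if both REGN2222 injections carry equal excess, and less if the excess sits in the second. First-dose tables are unaffected.

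No data are lost. The fault is that the column the SAP leads with and sorts by is the weaker one in these tables. That is worth correcting because the change is cheap and serves the SAP's own aim.

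**What to change.** In SAP 5.8.1, for acute tables timed from the second injection (2-day, 7-day, and injection-procedure-related events after the second dose):

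- Make REGN2222 2 doses versus placebo the lead contrast for signals and for sort order.
- Drop the combined column there, or footnote it as including Day 57 placebo injections.
- State that the 1-dose arm received placebo on Day 57, and show that arm separately. Any pooling of it with placebo should be supplementary and limited to acute injection reactions.

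In SAP 5.8.2, present acute hypersensitivity within 2 days and injection-site reactions separately for the first and second injection, pooling the REGN2222 arms for the first only.

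Keep the combined column for first-dose and whole-period tables. Record the change in SAP 1.2.3, which now lists no modifications, as a departure from Protocol 9.5.3.2.

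The cost is SAP wording, a few tables re-cut from data already collected, and one declared deviation. No new data and no change in trial conduct are needed.

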#### 7.2.2. Serious Adverse Events

All SAEs, regardless of assessment of causal relationship to study drug must be reported to the sponsor (designee) within 24 hours. Refer to the study manual for the procedure to be followed.

Information not available at the time of the initial report must be documented in a follow-up report. Substantiating data such as relevant hospital or medical records and diagnostic test reports may also be requested.

The investigator must promptly report to the Institutional Review Board/Ethics Review Committee (IRB/ERC) all unanticipated problems involving risks to subjects. This includes death from any cause and all SAEs related to the use of the study drug. It is recommended that all SAEs be reported to the IRB/ERC, regardless of assessed causality.

In the event the investigator is informed of an SAE after the subject completes the study, the following will apply:

- SAE with an onset within 30 days of the end of study/early termination visit the SAE will be reported to the sponsor. The investigator should make every effort to obtain follow-up information on the outcome until the event is considered chronic and/or stable.
- SAE with an onset day greater than 30 days from the end of study/early termination visit only fatal SAEs and those deemed by the investigator to be drug-related SAEs will be reported to the sponsor. The investigator will make every effort to obtain follow-up information on the outcome of a drug-related SAE until the event is considered chronic and/or stable.

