4.7. Safety Variables

Subject safety will be assessed through the collection of AEs, laboratory data (hematology, chemistry), vital signs, and physical exam (including weight). For these measures, with the exception of the AEs, all measurements will be assigned to analysis windows for temporal summaries. Unless otherwise noted (eg, AEs), baseline for these measures is defined as the last chronologically available valid assessment prior to the first dose of study drug.

The period of safety observation starts from the time when the informed consent is given and continues into the following periods:

- The PRE-TREATMENT period: defined as the day from the signed informed consent form (ICF) to before the first study drug injection.
- The SAFETY TREATMENT period: defined as the day from the first study drug injection up to the day of the last study drug injection plus 180 days.
- The POST-TREATMENT period: defined as starting the day after the end of the SAFETY TREATMENT period.

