evaluation - the day after the stop date of the initial episode of RSV illness + 1)/365.25. The end of efficacy evaluation is the last visit completed by a subject, scheduled or unscheduled, up to Visit 7. Negative binomial regression will be used to estimate the relative risk reduction associated with each REGN2222 arm as compared to placebo.

Categorical efficacy endpoints

RSV confirmed hospitalization, a component of the primary composite endpoint, will be explored using the same statistical methodology as the primary efficacy analysis. For this exploratory analysis, the two REGN2222 treatment groups will be combined for comparison to the placebo group, with the intent to evaluate the REGN2222 effect on subjects with RSV confirmed hospitalization.

Number and percentage of subjects taking medications associated with RSV or respiratory illness will be summarized by treatment group. The denominator used to calculate percentage will be the number of subject in the FAS assigned to each treatment group. The tables will be sorted by alphabetical order of ATC level 2 followed by ATC level 4.

The procedures associated with RSV or respiratory illness will only be listed for subjects in each treatment group.

The same CMH statistics as used in the primary approach for the primary efficacy variable will be used to analyze the following exploratory endpoints. Missing data will be addressed using the same same rules as used in the primary analysis for the primary efficacy variable (Section 4.6.1).

- Proportion of FAS subjects with the primary endpoint event, with the single exception of using an alternative definition for LRTI.
- Proportion of subjects with the primary endpoint event, with the single exception of the removal of RSV hospitalization non-LRTI

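### Exposure-adjusted adverse event rates count time after an infant has left the study, so they come out about 2–3% too low at the planned 5% dropout

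*SAP*

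**What the plan says.** SAP 5.8.1 introduces the rates this way: "Two event rate estimations adjusted by subject year of follow-up will be provided for all TEAEs by SOC and PT". Two denominators follow.

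- Rate 1 (events): "Total number of events divided by the total length of the TEAE period over all subjects in the SAF of each treatment group".
- Rate 2 (infants with the event): "For a subject with event, the time from first dose to the first event will be counted towards the denominator"; and "For a subject without event, the time from first dose to the end of the TEAE period will be counted towards the denominator".

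SAP 4.7 gives the safety treatment period as "defined as the day from the first study drug injection up to the day of the last study drug injection plus 180 days". SAP 4.7.1 equates this with the TEAE period, and protocol 9.5.3.3 has the same definition.

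Collection of events follows a different clock. Protocol 7.2.7 ends AE collection at the last study visit. Protocol 7.2.2 then covers an "SAE with an onset within 30 days of the end of study/early termination visit" if the investigator learns of it, and after that only fatal or drug-related SAEs.

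Elsewhere the SAP does end time at the last visit. SAP 4.5 derives the observation period to the last study visit. SAP 5.7.4 sets the limit for efficacy subject-years: "The end of efficacy evaluation is the last visit completed by a subject, scheduled or unscheduled, up to Visit 7". SAP 8 ends the TEAE period early in one case only: at the first-step analysis, infants classed as ongoing are cut at the data cut-off date.

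**The concern.** A rate per subject-year needs a denominator that covers the time in which an event could have been recorded. Here the numerator largely stops at the last visit, while the denominator runs on to a date fixed by the last injection. The longer the gap, the lower the reported rate, and for safety this error is in the favourable direction.

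The rates are planned for every system organ class and preferred term. Their label tells a reader that differences in follow-up have been allowed for. That allowance is missing for the infants whose follow-up was cut short.

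**Working it through.** **1. The plan's own figure.** A two-dose infant has 57 + 180 = 237 days, which is the protocol's stated treatment and follow-up duration; 28 + 57 + 180 = 265 days with screening also matches. An infant with one injection has 1 + 180 = 181 days. The documents state no AE rate or person-time, so the rest is a sensitivity calculation.

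**2. Inputs.** Dropout d = 5% (protocol 9.2, SAP 2.2). Assumed: completers have 237 days; withdrawal day t is uniform over Days 1–236 or Days 1–150; withdrawal before Day 57 means one injection (counted to Day 181), otherwise two (counted to Day 237).

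**3. Excess per withdrawn infant** = mean counted time − mean observed time.

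- Days 1–236: counted (56×181 + 180×237)/236 = 223.7; observed 118.5; excess 105.2 days.
- Days 1–150: counted (56×181 + 94×237)/150 = 216.1; observed 75.5; excess 140.6 days.

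**4. Rate 1.** SAP rate / rate on observed time = [(1−d)×237 + d×observed] / [(1−d)×237 + d×counted].

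| Withdrawals | d | Observed / counted mean days | Ratio | Too low by |
|---|---|---|---|---|
| Days 1–236 | 5% | 231.1 / 236.3 | 0.978 | 2.2% |
| Days 1–150 | 5% | 228.9 / 236.0 | 0.970 | 3.0% |
| Days 1–150 | 10% (assumed) | 220.9 / 234.9 | 0.940 | 6.0% |

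Example: 400 infants (about 1200 / 3), 20 withdrawn over Days 1–150, 100 events. Counted: (380×237 + 20×216.1)/365.25 = 258.4 subject-years, 38.7 per 100. Observed: (380×237 + 20×75.5)/365.25 = 250.7 subject-years, 39.9 per 100.

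**5. Rate 2.** Only withdrawn infants without the event add excess days. For a rare event that is nearly all of them, so step 4 applies. For a common event fewer do, and the excess in days falls. The denominator also shrinks, because infants with the event stop at the event, so the percentage need not fall. Suppose a constant event rate under which 20% of fully followed infants have the event, S(t) = exp(−λt), λ = −ln(0.8)/237. The mean of S(t)×(counted end − t) is 97.2 days (Days 1–236) or 131.8 days (Days 1–150). Mean observed denominators are 207.3 and 205.4 days. The ratios are 207.3/(207.3 + 0.05×97.2) = 0.977 and 205.4/(205.4 + 0.05×131.8) = 0.969. Rate 2 escapes only so far as withdrawn infants had already had the event.

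**6. Comparison between groups.** If withdrawal is equal in the groups compared, the rate 1 ratio is unchanged. As an illustration with no source in the documents, 10% v 3% (Days 1–150) gives 0.940/0.982 = 0.957.

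Equal dropout by randomised arm does not guarantee equality in the safety groups, because SAP 3.2 groups infants by REGN2222 doses received. An infant randomised to two doses who leaves before Day 57 joins the one-dose group. With 20 withdrawals per arm over Days 1–150, 20×56/150 = 7.47 infants move, each with 181 − 28.5 = 152.5 excess days.

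- One dose: (20×140.6 + 7.47×152.5)/(380×237 + 20×216.1 + 7.47×181) = 4.1% too low.
- Placebo: 20×140.6/(380×237 + 20×216.1) = 3.0%.
- Two doses: (20×140.6 − 7.47×152.5)/(380×237 + 12.53×237) = 1.8%.

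**The case against.** **The SAP is silent rather than wrong.** SAP 4.7 defines a window for classifying events and does not mention withdrawn infants. The word follow-up in SAP 5.8.1 points to actual follow-up, and SAP 8 ends the TEAE period and the observation period together for ongoing infants. The intent may well be right. Even so, SAP 5.8.1 names the TEAE period as the denominator, and that period has a stated end: "up to the day of the last study drug injection plus 180 days". A programmer who follows the text gets the wrong number. SAP 8 cuts at an administrative date, not at last contact. Read literally, it even treats an infant lost without an early-termination visit as ongoing to the cut-off.

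**Time after withdrawal is not wholly unobserved.** Protocol 4.2 requires follow-up of ongoing AEs and efforts at safety follow-up, and protocol 7.2.2 keeps some SAE reporting. This stands, so the added time is largely rather than entirely unobserved. Systematic AE collection still ends at the last visit.

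**Little depends on these rates.** This also stands. SAP 5.8 plans no formal safety testing, the many n (%) tables do not use this denominator, and disposition and length of observation are shown by group, so unequal dropout would be visible.

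**A reader might infer that an arm losing infants to adverse events would look safer.** The documents do not support that as a general claim. Infants who stop study drug are asked to stay for all remaining visits (protocol 5.2.2). Under rate 2, an infant withdrawn because of an event adds no excess time to that event's own rate. Rate 1 and the rates of other events remain exposed.

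**Conclusion.** Wrong as written, and small at the planned dropout. Both rates are biased downward because withdrawn infants keep adding time after AE collection has stopped. At 5% dropout rate 1 is about 2–3% too low, resting on the assumed even spread of withdrawals (105 or 141 excess days each) and on no recorded events after withdrawal. Rate 2 is affected only through withdrawn infants without the event: similar to rate 1 for uncommon events, with fewer excess days for common ones, though not necessarily a smaller percentage.

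The 10% and 10% v 3% cases are illustrations. The documents give no reason to expect such dropout or such an imbalance, and a reader should not infer that the safety conclusions are unsound. No formal comparison uses these rates. What the documents do support is that the rates do not deliver the follow-up adjustment they are labelled with, and that the shortfall differs between safety groups when withdrawal does.

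**What to change.** In SAP 5.8.1, for both rates, end each infant's time at risk at the earliest of: the end of the TEAE period; the last study contact (scheduled, unscheduled or telephone); death; and, at the first-step analysis, the cut-off date. For rate 2, add the first event. State that this also applies to infants lost without an early-termination visit, so that SAP 8 does not carry them to the cut-off as ongoing.

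The last study visit date already used in SAP 4.5 supplies most of the derivation. The definition of a treatment-emergent event in SAP 4.7.1 need not change. The cost is one SAP sentence, a minimum-of-dates step in the program, and slightly less favourable rates.
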